### **3. Phase 3 (Treatment Phase)**

Patients who satisfy symptom criteria in Phase 2 will be randomized in a 1:1 ratio to receive either a combination of colesevelam (1.875 gm twice daily) and clonidine (0.1 mg oral twice daily) or an identical placebo for 4 weeks. The randomization, to be prepared by [name], will be balanced on age (<50 vs. ≥ 50 y) and BMI (<30 vs. ≥ 30 kg/m^2). Patients will fill *daily* bowel diaries for the entire duration of the treatment phase and mail them in every week. Patients will be contacted periodically (by phone or email) to assess compliance with medications, with filling bowel diaries and for any adverse events. At the end of the treatment phase, patients will be asked to fill questionnaires pertaining to their quality of life and satisfaction with treatment. During the treatment phase, patients will be allowed to use rescue medication in the form of loperamide to circumvent the potential for withdrawal from the study due to overwhelming symptoms. Patients are allowed to take loperamide (2mg/dose) up to 3 unit doses in a 24 hour period, 5 unit doses in a 48 hour period or 10 unit doses in any 7-day period. Patients will need to record their loperamide usage in the bowel diary.

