### **4. Phase 4 (Post treatment phase)**

This phase, which lasts 4 weeks, will begin after patients take their last dose of medication. All patients who complete at least 1 week of treatment will enter this phase. During this phase, study staff will contact patients periodically by phone or email to enquire how they are doing. Patients will fill out daily bowel diaries for 4 weeks and return them weekly for review. At the end of 4 weeks, they will be asked to complete post-treatment questionnaires to assess quality of life, anxiety and depression. They will also be asked to collect a single spot stool sample and mail them in. The questionnaires will be used to investigate if patients had worsening of symptoms after stopping therapy. The spot stool sample will be used to analyze the effect of treatment on the fecal microbiota. Participants will be asked record their dietary intake for 72 hours prior to collecting the stool sample and mail in the food record.

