## **D. Human Subjects**

Only subjects who satisfy stringent inclusion and exclusion criteria and provide written informed consent will be included in the protocol. The consent form details issues related to privacy, withdrawal from studies, and use of blood for genetic analyses among other items. Additional details as follows:

1. **Anorectal assessments** are extremely safe; discomfort, if any during rectal distention is mild and tolerable and the risk of rectal perforation in an uninflamed rectum is negligible.
2. **Clonidine** is generally well tolerated at this dose. In a recent study, we observed that the most common side effect with clonidine was dry mouth (about 70% vs. 4.5% in placebo). Other adverse effects included drowsiness (23% vs 14% in placebo), light headedness (27% vs. 9% in placebo) and fatigue (36% vs. 23% in placebo) although they did not reach statistical significance.
3. **Colesevelam** is generally well tolerated at this dose. The most commonly reported side effects from Colesevelam are constipation, diarrhea, dyspepsia, hypoglycemia (mild and well tolerated), headache, abdominal cramps, nausea, and flatulence and back pain. Their frequency ranges from 8%-40% in different studies.

Patients will be appropriately screened and subjects with an increased risk of complications will be excluded from the study. All side effects will be recorded at the follow-up visit. Since the effects of clonidine and colesevelam in pregnant and nursing women are unknown, women who are pregnant or nursing will be excluded from the study. Women of child-bearing potential will be advised to employ contraceptive measures during the study and a pregnancy test will be checked before beginning clonidine or colesevelam.

Patients who cannot tolerate clonidine 0.1 mg bid will be switched to 0.1 mg once daily (qhs) Clonidine will be discontinued if:-

- (i) Subjects have syncope, or lethargy that interferes with safe performance of the volunteer's activities of daily living; or
- (ii) if the systolic blood pressure drops to < 90 mmHg for patients with a systolic BP between 90 and 130 mmHg, or if systolic BP falls to < 100 mmHg for subjects with a pre-treatment systolic BP > 130 mmHg; or
- (iii) if a subject becomes pregnant during the study.

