Patients who cannot tolerate three tablets of 625 mg colesevelam twice daily will have dose reduction by 1 tablet daily until they are able to tolerate the medication. Colesevelam will be stopped if a subject becomes pregnant during the study.

**Data Safety and Monitoring Plan.** The DSMP utilized will adhere to the protocol approved by the Mayo Clinic IRB. We propose the following plan: -

**Data quality and management:** The principal investigator will review all data collection forms on a three-monthly basis for completeness and accuracy of the data as well as protocol compliance.

**Adverse events grading:** The common grading scale listed below will be used to grade AEs:

- 0 No adverse event or within normal limits or not clinical significant
- 1 Mild AE, did not require treatment
- 2 Moderate AE, resolved with treatment
- 3 Severe AE, resulted in inability to carry on normal activities and required professional medical attention

- 4 Life threatening or disabling AE
- 5 Fatal AE

Attribution scale: An adverse event includes both, an expected side effect that is of a serious nature, or an unexpected side effect/ event regardless of severity. All events will be graded as to their attribution (unrelated to protocol, or possibly, probably, or definitely related to protocol). Any event that is reported to either the principal investigator or his designated research associates by the subject or medical staff caring for the subject and which meets the criteria will be documented as such.

**Data Monitoring.** The majority of data generated from these protocols will be from analyses performed in our laboratory or the immunochemical core laboratory. Standard quality control procedures are in place for each assay. The frequency of data review for this study differs according to the type of data and can be summarized in the following table:

Data type	Frequency of review
Subject accrual (adherence to protocol regarding demographics, inclusion/exclusion)	Weekly
Adverse event/safety rates (injuries)	Weekly
Annual report	Yearly for IRB

**4. DNA and RNA analyses.** DNA, RNA and plasma samples will be anonymized before being submitted to the genotyping or RNA Seq assays. Specific information is provided in the consent form regarding storage and future use of the biologic sample. These results will not be added to the written record.

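### The adverse-event definition leaves out expected non-serious effects, and how and when these are otherwise recorded is not pinned down, so tolerability may be captured unevenly and ungraded

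*Combined protocol and SAP*

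**What the plan says.** Section D (Human Subjects), under the Data Safety and Monitoring Plan, gives the definition: "An adverse event includes both, an expected side effect that is of a serious nature, or an unexpected side effect"; the unexpected kind counts at any severity. An event reported to the investigator or research staff "which meets the criteria will be documented as such". The same plan has a severity scale from 0 to 5, whose grade 1 reads "Mild AE, did not require treatment", an attribution scale, and a weekly review of adverse-event and safety rates.

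Earlier in section D, the protocol lists the known effects of both drugs and states: "All side effects will be recorded at the follow-up visit".

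On contact with patients, Phase 3 (Treatment Phase) says: "Patients will be contacted periodically (by phone or email) to assess compliance with medications, with filling bowel diaries and for any adverse events". Phase 4 (Post treatment phase) says that "study staff will contact patients periodically by phone or email to enquire how they are doing". Only patients with at least one week of treatment enter Phase 4.

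The Subject Safety paragraph of section C.4 adds that study staff monitor for side effects and that the principal investigator reviews them. The Data Analysis Plan and the list of endpoints in C.4 contain no comparison of side effects or adverse events between arms.

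**The concern.** The commonest harms to be expected here are the ones already known: dry mouth, drowsiness, light-headedness and fatigue from clonidine, and the effects listed for colesevelam. Because they are known, the definition admits them only when they are serious. Three features of the plan depend on the adverse-event label: severity grading, attribution and the weekly review. The Phase 3 contacts, the one collection route described during treatment, also use that term.

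What is at stake is the quality of the tolerability comparison. The documents cite no data on this combination in fecal incontinence. They also allow each drug to be reduced separately when it is not tolerated. If known effects are recorded at differing times, by differing questions and without grades, it will be hard to compare the arms or to relate symptoms to dose changes and withdrawal.

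**Working it through.** The plan states no figure on this point, so the check is mainly a reading of the passages together.

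**1. What the definition covers**

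| Type of effect | Serious | Not serious |
|---|---|---|
| Unexpected | adverse event | adverse event |
| Expected | adverse event | not an adverse event |

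The effects listed in section D fall in the lower row. When not serious, they are outside the definition.

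**2. What depends on the label.** The 0 to 5 grading, the attribution scale and the weekly review are all stated for adverse events. None is stated for side effects.

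**3. What else would capture these effects**

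- *Phase 3 contacts:* on safety they ask about adverse events. The interval is given only as periodic.
- *Phase 4 contacts:* a general enquiry, with no mention of adverse events or side effects. Patients with less than one week of treatment do not enter this phase.
- *Section D:* promises to record all side effects, at a follow-up visit. After Phase 1 the visible text describes phone or email contact, diaries mailed or returned weekly, and a mailed stool sample. Table 1 lists symptom instruments only. Figure 1 is not shown, so a visit drawn there cannot be excluded.
- *Subject Safety paragraph:* monitoring by staff and review by the investigator, with no question, form, schedule or grading.

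The intent to record is stated, but the method and timing are not.

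**4. What is analysed.** None of the secondary endpoints (a) to (o) is a comparison of side effects, and the Data Analysis Plan describes no safety table.

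**5. Scale, for illustration only.** Expected count = patients per arm × rate. The rates are those section D quotes from the earlier clonidine study. The arm sizes are 30 (60 women in the Abstract, randomized 1:1) and 33 (Power Statement).

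| Effect | Rates, clonidine vs placebo | 30 per arm | 33 per arm |
|---|---|---|---|
| Dry mouth | 70% vs 4.5% | 21.0 vs 1.35 | 23.1 vs 1.5 |
| Fatigue | 36% vs 23% | 10.8 vs 6.9 | 11.9 vs 7.6 |
| Light-headedness | 27% vs 9% | 8.1 vs 2.7 | 8.9 vs 3.0 |
| Drowsiness | 23% vs 14% | 6.9 vs 4.2 | 7.6 vs 4.6 |

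For example, 30 × 0.70 = 21.0 and 30 × 0.045 = 1.35. These are expected occurrences. The documents give no basis for saying how many would be missed.

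**The case against.** The strongest reply is that the definition governs a label, not what is written down. Events that meet it are documented as adverse events; nothing bars recording other side effects. Section D promises to record all of them, and the Subject Safety paragraph has staff monitor and the investigator review them with no limit by seriousness or expectedness. The dose-reduction provisions presuppose that staff learn of non-serious intolerance. Bowel effects such as constipation would also show in the daily diaries, kept in both arms during and after treatment.

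This stands against two stronger readings. A reader might infer that the commonest harms would go uncounted, or that the trial could not report a tolerability difference. The documents support neither, because the commitment to record and monitor side effects is part of the plan, and an unclear time of recording does not cancel it.

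A reader might also see a contradiction between the definition and the mild grade of the scale. There is none: an unexpected event counts whatever its severity, so a mild unexpected event takes grade 1.

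The reply does not remove the rest. The text does not confine the narrow definition to expedited reporting. The side-effect commitments carry no grading, attribution, standard question or schedule, and no analysis by arm follows from them.

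**Conclusion.** The point holds as a defect in definition and collection. Taken literally, expected non-serious effects are outside adverse-event classification, grading, attribution and weekly review. The plan means to record them by another route, but the visible text does not define that route's visit, interval or method, and no comparison by arm is planned. The likely result is uneven, ungraded capture rather than absence of data.

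The size of the loss cannot be stated. The illustrative counts show only that such effects would be frequent: about 21 versus 1 patients with dry mouth at 30 per arm, or 23 versus 1 to 2 at 33 per arm. They assume that the earlier clonidine rates apply to the combination. That most such events would be non-serious is a further assumption, since the documents do not give their severity or define what counts as serious. The conclusion on the follow-up visit is limited to the text and Table 1. The change should be made, since it is cheap and improves both safety review and the comparison of tolerability.

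**What to change.** - Define an adverse event as any untoward event after the first dose, whether or not expected and whatever its severity. Keep the narrower definition for expedited reporting only, and say so.
- Ask one standard question in both arms at each existing phone or email contact, state the interval, and include patients who stop early, among them those who do not enter Phase 4.
- Grade every event on the existing 0 to 5 scale.
- Reconcile the follow-up visit in section D with these contacts and with the monitoring described under Subject Safety.
- Add to the Data Analysis Plan a table of events by arm and grade.

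The cost is protocol wording, a slightly longer contact script and one more table. It needs no new visit or staff and leaves the dose and stopping rules untouched. A lighter alternative is to keep the definition and specify how side effects are asked about, recorded and graded. That would close the collection gap, but these effects would stay outside the weekly adverse-event review unless that review were widened too.
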